CALLiNGS Protocol: Care Across Locations Longitudinally of Goals and Symptoms

NCT : pending

June 23, 2018

Junior Faculty Career Development Award

**CALLiNGS Protocol: Care Across Locations Longitudinally in Navigation of Goals and Symptoms
Interdisciplinary Pediatric Telepalliative Consultations for Hospice Teams**

Project Abstract

Despite 35+ pediatric hospice discharges to rural providers each year in Nebraska; primary care providers, hospice directors, and hospice nurses in Nebraska report they feel unprepared to manage pediatric hospice patients. In this pilot intervention study guided by the Theory of Unpleasant Symptoms, web conferencing services will connect an inpatient pediatric palliative care team with adult outpatient hospice providers to support local providers in assessing pediatric-specific care needs and implementing developmentally-appropriate pediatric treatment plans for 10-20 medically-complex children. The objective of this CALLiNGS (Care Across Locations Longitudinally in Navigation of Goals and Symptoms) mixed-methods study is to test feasibility, acceptability, and quality of life outcomes from using web-conferencing technology to connect a hospital-based interdisciplinary pediatric palliative care with statewide field-based hospice teams during interdisciplinary meetings at a minimum of every 15 calendar days. The reason for selection of every 15 days is because Medicaid requires that interdisciplinary hospice teams meet at a minimum of every 15 days to review patient symptom burden, medications, and plan of care. The study team hypothesizes that telepalliative care for children has the potential to improve the quality of care delivered to pediatric palliative care patients in a rural state by facilitating the confidence and comfort of local providers, enhancing goals of care conversations, improving symptom management for patients and therefore quality of life for family members, and creating a unified and cross-setting shared care model. The study intends to determine whether direct patient-specific pediatric mentorship or general pediatric palliative education is more helpful for hospice staff, for patient symptoms, and for family quality of life. If feasible this model could transform the pediatric palliative care delivery in the state of Nebraska with expanded opportunity for application in settings with similar subspecialty provider shortages.

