Selection methods and sample size – Pediatric patients and their families will be informed of the CALLINGS Protocol (Care Across Locations Longitudinally in Navigating Goals and Symptoms) at time of home hospice enrollment to foster consecutive sampling enrollment. The local nurse team hospice will receive telehealth interdisciplinary team meetings specific to patient need for up to 60 minutes every 15 days. The pilot study size of 10-20 patients per hospice is grounded in evidence-base for feasibility study sample population size rather than power scales.⁴³ Note that study duration would be for a maximum of six months per enrollee (due to hospice enrollment being a six-month commitment as standard).

- Pediatric patient-specific case discussions for enrolled pediatric patients at hospice staff interdisciplinary team meeting every 15 days for 60 min sessions via telehealth

[figure not shown]
home hospice enrollment to foster consecutive sampling enrollment. The local nurse team hospice will receive telehealth interdisciplinary team meetings specific to patient need for up to 60 minutes every 15 days. The pilot study size of 10-20 patients per hospice is grounded in evidence-base for feasibility study sample population size rather than power scales.⁴³ Note that study duration would be for a maximum of six months per enrollee (due to hospice enrollment being a six-month commitment as standard).

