- **Consent/Enrollment** - Consent and enrollment procedures will follow strict Institutional Review Board expectations and ethical standard.
- **Stakeholder Survey** – Local hospice team will be asked about their perceived self-efficacy (comfort), knowledge, and perceived adequacy in caring for pediatric children in using quantified Pediatric Palliative Care Questionnaire scale pre- and post-child enrollment.

- *Symptom Burden and Quality of Life* – Child, guardian, and hospice team nurse will complete Pediatric PROMIS-37™ every 15 days to assess for symptom burden and translated quality of life.
- *Interdisciplinary (IDT) Telepalliative Care Meetings* –Technology Acceptance Model survey will occur every 15 days (in the pediatric palliative educational arm and in the patient-specific case discussion arm) as an automatic screen on the closing telepalliative screen to evaluate acceptability of technology interface. The reason for this frequency is that Medicaid requires that hospice interdisciplinary team interactions occur at a minimum of every 15 days.
- *Team Debriefing* – At enrollment and at the conclusion of the study period (six months per enrollee with total project duration 2 years) or within 3 days following a child’s natural end of life; the local hospice team members will be invited to engage in a qualitative interview with two thematic topics: 1. Please describe your experience caring for a pediatric patient and 2. Please describe your experience with telepalliative use. This interview will be recorded and coded for content using Atlas.ti software.

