Data Plan – Descriptive statistics will be computed for each outcome variable at each time point. Repeated measures ANOVA and trend plots will be used to explore quantified symptom burden and quality of life trends over time. The association between individual and multiple symptoms will be explored via linear and multiple linear regression. Bland-Altman plots will be used to assess concordance between symptom and quality of life reporting. Crude (unadjusted) associations between demographics (such as family economics, diagnosis, level of technology, delay to initial palliative care) and symptoms / quality of life will be explored via ANOVA or linear regression, as appropriate. A similar analysis will be used to explore the association between how hospice team self-perceived confidence and knowledge of pediatric palliative care and child symptom and quality of life. In the event the assumptions of the parametric tests identified above are violated, the appropriate non-parametric test will be used. When a non-parametric test is used, the median and interquartile range for continuous outcomes will be reported. A significance level of 0.05 will be used to judge statistical significance. In addition to monitoring for statistical significance, the study team will follow minimally clinically important

difference (MCID) for symptom burden or quality of life values over time.⁵⁸ MCID has been defined as “the smallest difference in a score of a domain of interest that patients perceive to be beneficial and that would mandate, in the absence of troublesome side effects and excessive costs, a change in the patient's management.”⁵⁹ Content of the two qualitative interview questions will be analyzed thematically using a qualitative coding methodology in Atlas.ti ([name] has completed graduate level qualitative coursework >9 credit hours and published >4 qualitative method manuscripts).⁶⁰

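### Relating hospice-team confidence to child outcomes by ordinary ANOVA or regression ignores that children share a team, so the false-positive rate can exceed 0.05

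*Combined protocol and SAP*

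**What the plan says.** The Data Plan first describes "Crude (unadjusted) associations between demographics" and symptoms or quality of life, which "will be explored via ANOVA or linear regression, as appropriate". It then extends the approach to the team: "A similar analysis will be used to explore the association between how hospice team self-perceived confidence and knowledge of pediatric palliative care" and the child's symptoms and quality of life. The threshold is general: "A significance level of 0.05 will be used to judge statistical significance".

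The predictor comes from the team. Under Stakeholder Survey, "Local hospice team will be asked about their perceived self-efficacy (comfort), knowledge, and perceived adequacy in caring for pediatric children", and Table 1 lists the hospice nurse team as completing the questionnaire.

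On how many children share a team, the documents disagree. Selection methods and sample size has "The pilot study size of 10-20 patients per hospice". The Project Abstract speaks of "developmentally-appropriate pediatric treatment plans for 10-20 medically-complex children", which reads as a total.

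On when the score is taken, Table 1 says enrollment and end of study. Stakeholder Survey says before and after child enrollment, which can mean a new score for each child.

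The documents do not give the number of hospice teams, an ICC, the unit of analysis, or the way staff answers become a team score. They name no random effect, cluster-robust variance or team-mean analysis.

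**The concern.** Ordinary ANOVA and linear regression take each child as an independent observation. If a team's score is attached to each of its children, one measurement is repeated across many rows and the standard error of the slope is too small whenever those children's outcomes are correlated. This is separate from the 15-day repeated measures: it remains after each child is reduced to one record. The Data Plan's non-parametric fallback does not help, because ordinary rank tests also assume independence.

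Some correlation within a team is plausible. The children share staff and region. Hospice nurses also supply proxy PROMIS ratings, so one team can generate both the confidence score and one version of the outcome.

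At stake is a spurious significant link between provider confidence and child symptoms. The central hypothesis names both among the expected benefits, so such a link could be read as support for it.

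**Working it through.** **Inputs from the documents.** Significance level 0.05 (Data Plan; taken as two-sided). Children per hospice 10-20 (Selection methods and sample size), or 10-20 in all (Project Abstract). Eligible children about 30 per year (Sample and inclusion criteria). Project duration 2 years (Team Debriefing).

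**Assumptions.** ICC of child outcomes 0.05, 0.1 and 0.3, because none is given. One record per child, no true association, equal team sizes.

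**Step 1: the plan's own figure.** With ICC = 0, or one child per team, simulated simple regression rejects in about 5% of runs (0.046-0.052). The nominal 0.05 is reproduced when children are independent.

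**Step 2: approximation under clustering.** For a score that is constant within teams of m children:

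- design effect: DEFF = 1 + (m - 1) × ICC
- effective sample size: number of children / DEFF
- false-positive rate: 2 × [1 - Φ(1.96 / √DEFF)]

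Example, 6 teams of 10 at ICC 0.1: DEFF = 1 + 9 × 0.1 = 1.90; effective sample 60 / 1.90 = 31.6; 1.96 / √1.90 = 1.42; rate 0.155.

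**Step 3: simulation.** 20,000 runs per setting, simple regression, score constant within team:

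| Teams × children | ICC 0.05 | ICC 0.1 | ICC 0.3 |
|---|---|---|---|
| 6 × 10 (60 children) | 0.10 | 0.16 | 0.33 |
| 4 × 5 (20 children) | 0.08 | 0.10 | 0.21 |
| 10 × 2 (20 children) | 0.06 | 0.06 | 0.09 |
| 20 × 1 (20 children) | 0.05 | 0.05 | 0.05 |

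The first row fits the per-hospice reading of the sample size; the others fit a total of 20.

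**Step 4: score retaken for each child.** If scores within a team correlate at 0.5 (assumed), DEFF becomes approximately 1 + (m - 1) × ICC × 0.5. For 4 × 5 this is 1.10, 1.20 and 1.60, and the simulated rates are about 0.06, 0.07 and 0.11.

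**Step 5: what a valid test has to work with.** Two years at 30 per year gives about 60 eligible children. At 10-20 per hospice that fills at most 60/20 = 3 to 60/10 = 6 teams. Regression on team means has (teams - 2) degrees of freedom, so 1 to 4. With two teams there are none, and with one team there is no contrast. In simulation, team-mean regression returned the error rate to 0.046-0.053 in every setting with three or more teams.

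**The case against.** The strongest reply is that the inflation depends on facts the documents do not supply. It needs a positive ICC and several children per team. Under the abstract's total of 10-20 children, spread over statewide teams with families 7 to 320 miles from the hospital, one to three children per team is plausible, and there the rate is near nominal. The score may also be retaken for each child. All of this stands, and it makes the point conditional. It does not remove it, because the sample-size section puts 10-20 patients in each hospice and the plan gives no method for that case.

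A reader might infer that the real sample is simply the number of teams. That is exact only as the ICC approaches 1. At 6 × 10 and ICC 0.1 the effective sample is about 32, between 6 teams and 60 children. The number of teams limits the degrees of freedom, which is a different statement.

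A reader might also infer that a clustered analysis would stop hospice differences in case mix or staffing from appearing as an effect of confidence. It would not. It corrects the standard error; confounding at team level remains.

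Finally, the study is labelled an exploratory pilot, its size rests on feasibility rather than power, and this association is not one of the three aims. No confirmatory conclusion depends on it. That limits the weight of the point, but the plan still applies a 0.05 threshold to the result and intends to publish.

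**Conclusion.** The point holds conditionally. As written, the analysis treats children of one hospice team as independent although the predictor is measured on the team, so its error rate can exceed 0.05. With a fixed team score and an assumed ICC of 0.05 to 0.3, the rate runs from about 0.10 to 0.33 for 6 teams of 10, and from 0.06 to 0.09 for 10 teams of 2. It is lower if scores are taken afresh for each child, and there is no inflation with one child per team or an ICC of zero.

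The unconditional statement that error exceeds 0.05 is not supported, because the documents give neither the ICC nor the number of teams, and leave both the children per team and the timing of the score open. The change should be made, but it concerns one exploratory association and not the study's main conclusions.

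**What to change.** 1. Reconcile the Project Abstract (10-20 children in total) with Selection methods and sample size (10-20 per hospice), and state the expected number of hospice teams.
2. State whether the questionnaire score is taken once per team or again for each child, and how staff answers are combined.
3. In the Data Plan, replace the reference to a similar analysis for this association. Regress the team's mean child outcome on the team score with (teams - 2) degrees of freedom. If scores vary by child, use a hospice random intercept with small-sample degrees of freedom.
4. With about five teams or fewer, show the plot and estimates without a p-value.
5. State as a limitation that other hospice differences may confound the association, whichever analysis is used.

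The cost is a few sentences of Data Plan wording and no new data. The price is a less favourable stated basis for this association: the test rests on the number of teams, perhaps 1 to 4 degrees of freedom under the per-hospice reading, and there may be no test at all.
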